7.2 Protocol Deviations

All recorded protocol deviations will be listed and summarised overall and by research centre.

The IPM Clinical Trial Physician(s) (one or more IPM physicians assigned to continually monitor trial data during the course of the trial) will establish protocol deviation criteria for the trial, in conjunction with the IPM Head of Quality Management and Compliance (QM&C), the Head of Biometrics and other clinical team members, as appropriate. The final list of protocol deviation criteria will be approved by the IPM Chief Medical Officer. Before database lock and statistical analysis, all reported protocol deviations will be reviewed by the IPM Clinical Trial Physician(s), Head of QM&C and Head of Biometrics, in conjunction with the trial statistician (from Clindata Research Innovation), to determine the impact of each deviation on the analysis, and to compile a final list of major protocol deviations for purposes of defining the PP analysis population. The final list will be signed off by the IPM Chief Medical Officer.

Major protocol deviations that will result in exclusion of a participant from the PP analysis will include:

- Inappropriate enrollment into the trial (e.g. participant met an exclusion criterion, or participant failed to meet all inclusion criteria) as documented in the Deviations Log (DL) CRF. A major deviation will exclude the participant completely from the population.
- IP-related deviations (e.g. IP was incorrectly withheld from participants, participants incorrectly resumed IP use, or inappropriate IP was dispensed to a participant). The data of such participants will be censored at the date of the last negative HIV-1 test result prior to the occurrence of the deviation.
- The participant demonstrated non-adherence to IP use, evident from any missed 3-monthly research centre visits. The data of such participants will be censored at the date of the last negative HIV-1 test result prior to the first missed 3-monthly visit.
- Any other major protocol deviation identified during review of the data that may impact the integrity of the data. The decision whether the participant should be excluded entirely from the population or whether the data of the participant should be censored will be made during the review of the protocol deviations.

The number of participants with minor and major protocol deviations will be presented using appropriate summary statistics, overall and by research centre.

7.3 Adherence to Ring Regimen

The data collected in IPM 032 allows for both objective and subjective assessments of adherence to ring use by the participants in this trial.

Dapivirine residual levels in returned used rings are used as objective, quantitative measure of adherence to ring use in this trial.

Subjective adherence measures include self-reported ring use as collected on the Accidental Expulsion/Removal Log (EXP) CRF. Missed clinical trial visits are also used as an indicator of non-adherence to prescribed product use.

7.3.1 Dapivirine Ring Residual Levels in Used Rings

A comprehensive description of the planned analysis of dapivirine ring residual levels is provided in Section 9.2.

7.3.2 Self-reported Adherence

A comprehensive description of the planned analysis of self-reported adherence to the ring regimen is provided in Section 9.4.4.

8 EVALUATION OF DEMOGRAPHIC AND BASELINE CHARACTERISTICS

Unless otherwise specified, baseline characteristics, including medical history (MED), contraceptive/menstrual/obstetric history (CMO), and gynaecological history (GHXL) obtained

at the Screening and Enrollment visits, will be summarised descriptively, overall and by research centre, using appropriate summary statistics as described in Section 6.6.

8.1 Baseline Demographics

The following baseline demographic characteristics will be listed and summarised: age, race, height, weight and body mass index (BMI), education level, relationship status, current residential status with main sex partner, information on vaginal sex once a week or more, usual number of vaginal sex acts, genital STIs at baseline, number of male sex partners at baseline, partner knowledge of ring use and whether the participant has children or not. Age and BMI will be derived as described in Table 1 below.

Table 1 Derived and Computed Demographic Variables

Variable Name	Description	Computation Methods, Notes, or Equation(s)
Age	Age (years)	INT((date of enrollment – date of birth)/365.25)
BMI	Body Mass Index (kg/m ²)	(Participant body weight in kg)/ (Participant height in m) ²

Qualitative demographic characteristics (nominal or ordinal categories) will be summarised using absolute and relative frequencies. Quantitative demographic characteristics (continuous) will be summarised using the appropriate summary statistics, namely number of participants, mean, SD, quartiles, and range.

The demographic characteristics will be summarised by research centre, IPM 027 treatment arm, seroconversion status and overall. An additional table will be created to summarise the demographic characteristics by research centre, overall and IPM 032 enrollment status (IPM 027 participants enrolled into IPM 032 vs not enrolled in IPM 032).

All demographic and baseline characteristics will be presented in participant listings.

8.2 Baseline Medical History

Medical history will be collected during the Screening visit and Trial Visit 0 (pre-enrollment). Medical history will be presented in tabular form using appropriate descriptive statistics. All medical history will be listed.

8.3 Baseline Screening Assessments

Laboratory assessments conducted at baseline, including cytology, syphilis testing (Rapid Plasma Reagins [RPR]; confirmatory Treponema Pallidum Haemagglutination Test/Treponema Pallidum Particle Agglutination Assay [TPHA/TPPA]), haematology, biochemistry, urinalysis, urine pregnancy tests, and HIV rapid tests will be presented for all participants. General physical examination and pelvic examination results will be presented at the Screening visit for all participants.

Obstetrics and gynaecological history will be collected during the Screening visit, and gynaecological conditions will be coded using Version 19.0 of the Medical Dictionary for Regulatory Activities (MedDRA). Obstetrics and gynaecological history will be presented in tabular form with absolute and relative frequencies, and gynaecological conditions will be classified using System Organ Class (SOC) and Preferred Term (PT).

8.4 Prior Therapies and Medications

Prior medication is defined as any medication that started and ended before the first insertion of IP. Medications will be coded using the World Health Organization Drug Dictionary Enhanced (WHO DDE) (version June 2017). A table summarising the number and percentage of participants using drugs, by Anatomical Therapeutic Chemical (ATC) level 2 classification and preferred name, will be presented.

9 EVALUATION OF TRIAL ENDPOINTS

9.1 Primary Endpoint 1 – Safety

The analysis of AEs will be mainly descriptive in nature. That is, the number and percentage of participants experiencing AEs will be presented per SOC and PT, overall and by research centre. The proportion of participants experiencing the following will be determined and summarized:

- AEs considered by the Investigator as related to IP
- Grade 3 or 4 AEs
- SAEs

For these three endpoints, and for the most frequently reported AEs (*i.e.* AEs occurring in at least 5% of participants overall) the proportion and the corresponding 95% confidence interval will be presented for the overall counts. The confidence interval will be determined using Fisher's exact test.

Separate tabulations will be created for AEs of special interest (selected urogenital AEs and STIs). For this purpose, PTs may be grouped into categories of interest (refer to Appendix 5).

9.2 Primary Endpoint 2 – Adherence

Dapivirine residual levels in used rings will be determined for all participants receiving IP, as a measure of adherence to ring use. The data will be listed, summarised and presented graphically, as described below.

Dapivirine Residual Levels in Used Rings

All used vaginal rings that are returned to the research centres at each trial visit are collected and shipped at regular, pre-defined intervals to an analytical laboratory,

where the rings are analysed to determine the residual amounts of dapivirine in the rings.

For this trial, a reported ring residual level of > 23.5 mg dapivirine will be used as an indication of non-adherence to ring use over the 30-day period (± 7 days) that a woman was to keep the ring *in situ*. Based on the data from the Phase III program, the cut-off value of > 23.5 mg for dapivirine ring residual levels was shown to be a good measure of non-adherence to ring use, indicating no or very little ring use.

The following summaries and graphical presentations will be produced for these data:

- A summary of ring residual levels at each trial visit and at the time of seroconversion, the time of first HIV-1 RNA positive as well as the time of last HIV-1 RNA negative will be presented with standard descriptive statistics – presented overall, by IPM 027 treatment arm, and by research centre. Corresponding box plots will be prepared.
- A descriptive summary of the ring residual levels by trial visit and by category of residual amount (< 20 mg, $20 – 21$ mg, $> 21 – 22$ mg, $> 22 – 23.5$ mg, and > 23.5 mg). This summary will be prepared overall, by IPM 027 treatment arm and by research centre, with corresponding bar charts.
- A summary relating the ring residual levels to time intervals (in days) between consecutive ring replacements (< 23 days, $23 – 37$ days, $> 37 – 84$ days, and > 84 days). Corresponding box plots will be prepared.

Note: All summaries and graphical presentations will be produced for both uncorrected dapivirine ring residual levels (as reported by the analytical laboratory) and residual levels corrected for manufacturing and assay variability, unless otherwise specified.

The aforementioned graphical presentations will be repeated for the ring residuals from the IPM 027 and IPM 032 trials, and will be based only on the participants from IPM 027 who enrolled in IPM 032. However, only the uncorrected ring residual levels will be used.

In addition, a listing will be produced for those trial participants who HIV-1 seroconverted, with HIV-1 infection estimated to have occurred on IP, listing the date of the last negative HIV RNA PCR test, the date of the first positive HIV RNA PCR test, the number of days in-between, the time to first positive HIV-1 RNA, the corresponding corrected and uncorrected dapivirine ring residual levels, and the appearance and colour of the rings.

A summary table, listing and scatter plot of the residual levels of dapivirine in the last three rings returned by these participants prior to HIV-1 seroconversion will be produced and compared visually with the average ring residual levels of those participants who remained HIV-negative over the duration of the trial. If possible, the

summary table and plot will also be produced by categories of the appearance and colour of these rings.

Finally, a summary table, listing and scatter plot of the residual levels of dapivirine in the last two rings prior to the first positive HIV-1 RNA will be produced and compared visually with the average ring residual levels of those participants who remained HIV-negative over the duration of the trial.

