Residual levels of dapivirine in returned rings and/or plasma and/or vaginal fluid concentrations of dapivirine will be used as measures of adherence to ring use. The data will be listed, summarised and presented graphically. Participants will be categorized as either adherent or non-adherent, based on these measures. The ring residual levels and/or plasma and/or vaginal fluid concentrations of dapivirine associated with non-adherence will be informed by the results from IPM 027, and will be described in detail in the SAP, which will be finalised prior to final database lock. The correlation between the amount of residual dapivirine in the used rings and the corresponding plasma and/or vaginal fluid levels of dapivirine will be explored graphically and summarised descriptively.

8.4.3. *Secondary Analyses*

8.4.3.1. *Incidence of HIV-1 seroconversion*

The incidence of HIV-1 seroconversions, the incidence density rate of HIV-1 seroconversion, i.e. HIV-1 seroconversion rate per 100 woman-years of product use at the end of the ring use period, as well as a 95% CI for the HIV-1 seroconversion rate per 100 woman-years based on the normal approximation of the Poisson distribution will be presented for each research centre, and overall. Kaplan-Meier curves will be presented, stratified by research centre.

8.4.3.2. *HIV-1 drug resistance*

The analysis of HIV-1 drug resistance will be primarily descriptive in nature, and will depend on the pattern of resistance mutations observed in the HIV-1 seroconverters. The resistance associated mutations observed will be listed by participant, and a frequency tabulation of individual resistance mutations associated with the various

classes of antiretrovirals, e.g. Protease Inhibitors, Nucleoside Reverse Transcriptase Inhibitors and Non-nucleoside Reverse Transcriptase Inhibitors, will be produced. The proportion of HIV-1 seroconverters with at least one HIV-1 drug resistant mutation will be presented, with the corresponding 95% CI.

8.4.4. *Interim Analysis*

No interim analysis is planned for this trial. However, the Sponsor will review the treatment emergent safety data at regular intervals during the conduct of the trial.

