6.2 Methods for Handling Missing Data

While every effort will be made to minimise the amount of missing data, some degree of missing data, primarily associated with missed visits, is expected. The amount of missing data will be explored and incorporated into the analyses, where appropriate. For the analysis of adherence to monthly ring use, patterns of missing data may be informative. Depending on the proportion of participants who discontinue early, an analysis of time to discontinuation may be conducted. Such an analysis would allow investigation of the covariates associated with early discontinuation. Patterns of missing data may also provide further insight into participants' preference for monthly or 3-monthly follow-up visits to research centres.

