At all trial visits and the last product use visit, the RL CRF will be completed, indicating the rings dispensed at each trial visit (items 1 and 2) and the used / unused rings returned at each trial visit (items 7 and 8).

Statistical methods

The analysis of feasibility of the 3-monthly clinical follow-up schedule will be primarily descriptive in nature, and will include absolute and relative frequencies for each trial visit for Participant Questionnaire items listed above, overall and by Visit Schedule (A, B or C). In particular, the number and percentage of women opting not to receive two additional rings at the 3-monthly clinical follow-up schedule will be reported.

The proportion of returned rings (used and unused) during the 3-monthly clinical follow-up schedule will also be reported. This will be calculated as the number of used/unused rings returned divided by the number of rings dispensed.

9.4.2 Exploratory Endpoint 2: Correlation between dapivirine residual amounts in returned used vaginal rings and/or drug concentrations, and results from visual inspection of returned vaginal rings

Consistent with exploratory objective 2, exploratory endpoint 2 is the dapivirine ring residual levels in returned used vaginal rings and/or dapivirine concentrations in plasma and/or vaginal fluid (not assayed) in correlation with results from the visual inspection of the returned used vaginal rings by research staff.

Assessments

At all trial visits and the last product use visit, the RL CRF will be completed, indicating the rings dispensed at each trial visit (items 1 and 2) and the appearance of used/unused rings returned at each trial visit (items 7, 8 and 9).

Residual levels of dapivirine in used rings will be determined for all participants receiving IP at each trial visit.

Statistical methods

The correlation between the amount of corrected residual dapivirine in the used vaginal rings and the corresponding results from the visual inspection of the returned used vaginal rings, will be explored descriptively by producing summary statistics and

a corresponding scatter plot of the dapivirine levels for each category of appearance and colour of the returned ring.

9.4.3 Exploratory Endpoint 3: Proportion of participants opting for HIV rapid tests at the research centre between scheduled 3-monthly visits

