Subgroup: All IPM 032 participants										
Month Ring Used	Trial	n	Mean	Q1	Median	Q3	SD	Min	Max	95% CI ^b
Enrolment / Trial Month X	IPM 032 / IPM 027	XXX	XX.X	XX.X	XX.X	XX.X	XX.XX	XX	XX	XX.X, XX.X
		XXX	XX.X	XX.X	XX.X	XX.X	XX.XX	XX	XX	XX.X, XX.X

Programmers Note: Please repeat table for the following Subgroups: Marital status: Married; Marital status: Unmarried; Age < 25 years; Age ≥ 25 years; Main sex partner: Yes; Main sex partner: No; Presence of genital symptoms/STIs: Yes; Presence of genital symptoms/STIs: No (Note that the number of participants (n) should reflect the number of participants in each subgroup)

CI = Confidence interval

^b 95% CI for the mean

Centre 01: Madibeng Centre for Research (MCR); Centre 02: MatCH Research Unit (MRU); Centre 04: Qhakaza Mbokodo (QM);

Centre 06: MRC/UVRI & LSHTM Uganda Research Unit (MRC/UVRI); Centre 07: Desmond Tutu HIV Foundation (DTHF), Masiphumelele; Centre 08: Ndlovu Care Group (NC

Table 14.3.5.2
 Adherence, Summary of Dapivirine Residual Levels (mg) in Used Rings by Category
 Safety Population

Month Ring Used	Trial	All Rings	0 - < 20 mg n (%) ^a	20 - ≤ 21 mg n (%) ^a	> 21 - ≤ 22 mg n (%) ^a	> 22 - ≤ 23.5 mg n (%) ^a	> 23.5 mg n (%) ^a
Enrolment / Trial Month X	IPM 032 / IPM 027	XXX	X (X.X)	X (X.X)	X (X.X)	X (X.X)	X (X.X)

^a Percentages are calculated out of the total number of rings per trial month

Centre 01: Madibeng Centre for Research (MCR); Centre 02: MatCH Research Unit (MRU); Centre 04: Qhakaza Mbokodo (QM);
 Centre 06: MRC/UVRI & LSHTM Uganda Research Unit (MRC/UVRI); Centre 07: Desmond Tutu HIV Foundation (DTHF), Masiphumelele; Centre 08: Ndlovu Care Group (NCG)

Table 14.3.5.3
Adherence, Summary Relating Ring Residual Levels (mg) to Time Intervals Between Consecutive Ring Replacements
Safety Population

Month Ring Used	Time Interval Between Consecutive Ring Replacements for Residual Levels in Ring	n	Mean	Q1	Median	Q3	SD	Min	Max
Enrolment / Trial Month X	< 23 days	XXX	XX.X	XX.X	XX.X	XX.X	XX.XX	XX	XX
	23 – 37 days	XXX	XX.X	XX.X	XX.X	XX.X	XX.XX	XX	XX
	> 37 – 84 days	XXX	XX.X	XX.X	XX.X	XX.X	XX.XX	XX	XX
	> 84 days	XXX	XX.X	XX.X	XX.X	XX.X	XX.XX	XX	XX

Table 14.3.5.4
Residual Levels of Dapivirine (mg) in the Last Three Rings Returned by Participants Who Seroconverted, Prior to HIV-1 Seroconversion
Safety Population

Appearance Colour	Statistic	HIV + (N=XXX)	HIV - (N=XXX)
Used			

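### The primary adherence summary covers only used rings that came back, so expected months with no ring inserted drop out of the denominator

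*SAP*

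**What the plan says.** Under SAP 9.2, "All used vaginal rings that are returned to the research centres at each trial visit are collected and shipped" to a laboratory that measures residual dapivirine, and "a reported ring residual level of > 23.5 mg dapivirine will be used as an indication of non-adherence to ring use". Table 14.3.5.2, headed as a table of used rings, sorts rings into five residual bands. Its footnote reads: "Percentages are calculated out of the total number of rings per trial month". The footnote does not say which rings make up that total. The table title and the residual-only columns make assayed rings the natural reading.

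Plasma and vaginal fluid samples were not assayed (SAP 2.4), so ring residuals are the only objective measure of use.

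Other parts of the plan touch on rings or months without an assay:

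- SAP 6.2: "For the analysis of adherence to monthly ring use, patterns of missing data may be informative". No rule follows for the adherence tables.
- SAP 7.3: "Missed clinical trial visits are also used as an indicator of non-adherence to prescribed product use". SAP 7.2 lists among the major deviations: "The participant demonstrated non-adherence to IP use, evident from any missed 3-monthly research centre visits". That entry governs censoring in the per-protocol population.
- SAP 9.4.1, on the proportion of rings returned in the 3-monthly schedule: "This will be calculated as the number of used/unused rings returned divided by the number of rings dispensed".
- SAP 9.2 and Table 14.3.5.3 relate residuals to the days between ring replacements, with bands up to more than 84 days.
- SAP 9.4.4 counts the expected days of self-reported wear from the insertion date.

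Protocol 8.4.2 also promises that "Participants will be categorized as either adherent or non-adherent, based on these measures". SAP 9.2 gives no participant-level rule, so any such classification would rest on the same rings.

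**The concern.** The primary objective is adherence to a ring inserted every month. The summary answers a narrower question: among used rings that came back, how many show little or no release. A month in which the ring stayed in its package supplies no used ring, so a month of certain non-use is removed rather than counted.

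This is not spread evenly over the trial. At centre visits the ring is inserted under supervision (Protocol 5.14). On the 3-monthly schedule three rings are dispensed and two are normally inserted at home (Protocol 4.3 and 5.13). Non-insertion is therefore mainly possible on the schedule whose feasibility the trial sets out to explore. A primary endpoint could look better than actual use, and the monthly and 3-monthly phases could look alike when they are not.

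**Working it through.** **No figure to reproduce.** The documents state no return rate and no expected share of rings above 23.5 mg. The check is therefore bounds arithmetic on assumed values.

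**1. Where the exposure lies.** Ring-months follow from the visit schedules in SAP 6.6, taking the last visit before Exit as the end of ring use and assuming that the take-home option is used.

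- Schedule A (months 1, 4, 7, 10, 13): 1 + 4×3 = 13 ring-months, of which 12 (92%) are in the 3-monthly phase; home insertions 4×2 = 8 (62%).
- Schedule B (months 1, 2, 5, 8, 11, 14): 2 + 4×3 = 14, of which 12 (86%); home insertions 8 (57%).
- Schedule C (months 1, 2, 3, 6, 9, 12): 3 + 3×3 = 12, of which 9 (75%); home insertions 6 (50%).

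**2. One participant.** In a 3-month interval a woman wears one ring throughout and never inserts the other two. Her one assayed ring is at or below 23.5 mg. The measure shows 1/1 = 100% adherent; over expected ring-months it is 1/3 = 33%.

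**3. Bounds.** Let r be the share of expected ring-months with an assayed ring, q the share of assayed rings above 23.5 mg, and a the true adherence in the ring-months without an assay.

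- Reported adherence = 1 − q, whatever r is.
- True adherence = r(1 − q) + (1 − r)a.
- Reported minus true = (1 − r)(1 − q − a), so the measure overstates when a < 1 − q.
- Worst case (a = 0) = r(1 − q). Best case (a = 1) = r(1 − q) + (1 − r).

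For a month with no ring inserted, a = 0 and overstatement is certain. For a ring worn and then lost, a may be 1.

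With q = 10% (assumption), reported adherence is 90% in every row:

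| r (assumption) | Worst case | Best case |
|---|---|---|
| 95% | 85.5% | 90.5% |
| 90% | 81.0% | 91.0% |
| 80% | 72.0% | 92.0% |
| 70% | 63.0% | 93.0% |

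Over q from 5% to 20% and r from 70% to 95%, the largest possible overstatement, (1 − r)(1 − q), runs from 4.0 to 28.5 points. The largest possible understatement, (1 − r)q, runs from 0.3 to 6.0 points.

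**4. By phase.** Suppose that only home-inserted rings are missing, at 20%, and q = 10% (assumptions). Reported adherence is 90% everywhere. The worst case among home-inserted rings is 0.80 × 0.90 = 72.0%. Overall it is (13 − 1.6)/13 × 0.90 = 78.9% for Schedule A and (12 − 1.2)/12 × 0.90 = 81.0% for Schedule C.

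**The case against.** The strongest replies are these.

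- **The plan already shows skipped replacements.** The woman in step 2 would have an interval of about 90 days and fall in the band above 84 days of Table 14.3.5.3. This stands in part: the table exposes the pattern, but it describes residuals by interval and adds no skipped month to the adherence percentages. The return proportion and the missed-visit indicator also show part of the gap without entering those percentages. The return proportion pools used and unused rings, so a ring handed back unopened raises it.
- **Some uninserted rings are assayed.** Tables 14.3.5.4 and 14.6.2 report residuals for rings that look unused. A ring never inserted but handed back as used would be assayed and should exceed 23.5 mg. This stands. The firm loss is narrower: rings handed back as unused (unless the plan means these to be assayed), rings never returned, and months with no ring dispensed.
- **Unreturned rings may have been worn.** The reasons recorded in Listing 16.2.5.4, such as loss, flushing or discarding, are compatible with use, and Protocol 6.5 lets a woman on the 3-monthly schedule use a spare. This stands, and it leaves the direction open for those rings.
- **The endpoint follows the protocol and is descriptive.** Protocol 2.2 names residuals in returned rings, and SAP 6.3 calls the analysis descriptive. True, but a descriptive percentage still needs a denominator that matches its objective.

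A reader might go further and conclude that adherence as a whole is overstated, or that every unopened or missing ring is a non-adherent month. With q = 10% and 10% of rings missing, that would turn 10% non-adherence into 0.10 + 0.90 × 0.10 = 19%. The documents do not support this: 19% is only the worst case. Nor are rings dispensed the right denominator. They include spares and replacements, and rings retrieved or withheld under protocol-directed holds or at discontinuation (Protocol 5.4.3, 5.6, 6.5, 6.6), and they miss months in which none was dispensed.

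**Conclusion.** The concern holds in this form. The primary adherence summary is conditional on a used ring being returned and assayed, and no rule brings in the other expected ring-months. Where no ring was inserted, the month is lost and adherence is overstated for it. Where a ring was not returned, the direction is unknown and adherence can be overstated.

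The size cannot be stated from the documents. With 10% of assayed rings above 23.5 mg and an assayed ring for 90% of expected ring-months, both assumptions, reported adherence is 90% and the truth lies between 81% and 91%. The room for overstatement (9 points) is much larger than the room for understatement (1 point), but that shows what is possible, not what happened. The 3-monthly phase is the most exposed because most home insertions depend on it.

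**What to change.** In SAP 9.2, Table 14.3.5.2 and its bar charts, add a summary with expected ring-months on product as the denominator.

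- Derive expected ring-months from the ring log and visit data. Exclude protocol-directed holds, time after discontinuation, and spare or replacement rings.
- Count a month with no ring inserted (recorded as not inserted, or package unopened) as non-adherent.
- Show not returned, and not dispensed (for example after a missed visit), as separate categories, with worst-case and best-case bounds.
- Present the result by visit phase, monthly against 3-monthly.
- State whether rings returned as unused are assayed, and define the ring total in the footnote to Table 14.3.5.2.
- Keep the returned-ring table alongside.

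Listing 16.2.5.4 already carries insertion status, package status, return status and the reason for non-return, so no new data are needed. The cost is some extra programming and a possibly less favourable adherence figure.
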